## 4.2 Power consideration

In this study, a total of 66 patients (allocated in a 2:1 ratio: immunoabsorption (IA) group: 44 patients vs. sham group: 22 patients) will be included. Limited data from 2 small pilot studies, investigating IA in 10 patients with CFS/ME, is available to date. Consequently, data is lacking about precise effects, clinical outcomes, and effect sizes in this group of patients.

The justification of the sample size is based on the primary endpoint (change from baseline of the Chalder Fatigue Scale). The Chalder Fatigue Scale measures fatigue in patients using the overall score (range from 0 to 33) derived from a questionnaire with 11 questions (each scored from 0 to 3, see (Cella & Chalder, 2010; Chalder et al., 1993) for more details). Based on Cella & Chalder 2010, the mean score in a population of patients

suffering from CFS is 24.4 (with a standard deviation of 5.8) and for a healthy sample a mean value of 14.2 (with a standard deviation of 4.6) was observed. A difference of 10 points cannot be expected in this study since only patients suffering from CFS are included. In the systematic review of Nordin et al. 2016 a minimal important difference for the global change ranges between 2.3 and 3.3.

In an earlier study (Cleare et al. 1999) examining the efficacy of various treatments for CFS/ME, the difference in means of the Chalder Fatigue Scale was 4.5 points (Likert score) between the active and the control group. However, no sham-controlled study evaluating the effect of IA on CFS/ME has been conducted so far, but first pilot studies suggest a positive effect of IA in patients with CFS/ME.

To explore the expected precision obtained from the planned study, the distance from the mean group difference of the primary endpoint (change from baseline in Chalder Fatigue Scale) to the limits is calculated using its 95% confidence interval (CI) and a common standard deviation of 5.8 as provided for patient with CFS/ME in (Cella & Chalder, 2010). Using these assumptions and the given group sample sizes of 44 patients and 22 patients, the distance from mean to the limits of the 95%-CI is 3.03 points in the Chalder Fatigue Scale. Assuming an expected drop-out rate of 20% (resulting in expected group sample sizes of 35 and 18 patients, respectively) the distance from the mean to the limits of the 95%-CI increases to 3.37 points in the Chalder Fatigue Scale.

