### 5.2 Application

The primary analysis is performed using the full analysis set (FAS), including the estimated values from multiple imputations for missing values. An analysis of the primary outcome using the PPS is used as a sensitivity analysis. All safety analyses will be done using the SAS (Safety analysis set).

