- IgM Expression: Mean fluorescence intensity (MFI) on total CD19 $^{+}$  B cells, Percentage of IgM $^{-}$  cells within the CD19 $^{+}$  gate, IgM MFI and %IgM $^{-}$  specifically on

IgDCD27+ memory B cells (CD19+IgDCD27+ gate), Activated Canonical Class-Switched Memory B Cells (aCSM), CD19+IgDIgMCD27+CD11c, Frequency quantification within total B cells or parent gates, Activated canonical class-switched memory B cells

Table 5: primary and secondary outcome variables

| Characteristic   | Variable            | Values   |
|--|---------------------|--|
| Primary outcome variable   |                     |  |
| Chalder Fatigue Scale at 2 months  | cfs_0001-cfs_0011   | 11 items with levels 0-3 each, sum score has to be calculated  |
| Secondary outcome variables  |                     |  |
| Efficacy related outcomes  |                     |  |
| Chalder Fatigue Scale at End of Treatment (EOT) visit and at month 1, 2, 4, and 6 after the completion of IA | cfs_0001-cfs_0011   | 11 items with levels 0-3 each, sum score has to be calculated  |
| Post-COVID-19 Functional Status (PCFS) scale   | pcfs_0020-pcfs_0050 | Ordinal scale, range 0 to 4 (0: no limitations, 4: severe limitations),  |
| SF-36 physical domain  | sf_0041-sf_0050     | 10 items, each scored with: no limitations (0 points), some limitations (5 points), severe limitations (10points), the sum will be calculated  |
| Fluge questionnaire  | ccc_0011-ccc_0131   | 5 domains with different number of items, domains: fatigue, pain, cognition, circulation, each item is scored from 0 to 10 according to the severity (10: highest severity), domains will be analyzed separately |
| Post-Exertional Malaise (PEM)  | pem_0021-pem_0110   | 11 items, 5 items scored 0 to 4 for frequency, 5 items scored 0 to 4 for severity, 1 item scored 0 to 6 for duration, sum score from 0 to 46   |
| Bell Score   | bell_0020           | 1 item with 11 statements, 0-100   |

|  |  |  |
|--|--|--|
|  |  | points (100: no symptoms, 0: severe symptoms)  |
| Compass-31   | com_0001-com_0031  | 31 items in 6 domains, score by domain are rescaled ranging from 0 to 100  |

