| Schellong Test /POTS   | pst_0021-pst_0080  | Using items to evaluate if POTS is present (Increase in heart rate within 10 minutes of standing by at least 30 beats/minute above the level when lying down or, to at least 120 beats/minute absolutely, no pathological drop in blood pressure (i.e., systolic drop not more than 20 mm Hg and diastolic drop not more than 10 mm Hg), increasing symptoms of orthostatic intolerance) |
| 6 Minute Walking Test (6 MWT)  |  |  |
| MoCA   | moca_0011-moca_0110  | Score items, sum of maximum 30 or 31 points dependent on educational level   |
| Symbol Digit Modalities Test, SDMT   | sdmt_0020  | Item on number of correct remembered words after 90 seconds  |
| PROMIS-29, physical function, anxiety, depression, pain interference, pain severity, fatigue, sleep disturbance, ability to participate in social roles and activities | pfa11-pfa53, edanx01-edanx53, eddep04-eddep41, hi7, an3, fatexp41, fatexp40, sleep109, sleep116, sleep20, sleep44, srpper11_caps-srpper46_caps, pain9-pain34, global07 | each of the 7 domains will be scored separately, transformation in standardized t-values   |
| PROMIS cognitive function short form 4a  | pc2r-pc42r   | Sum score converted to t score   |
| Additional secondary outcome variables   |  |  |
| VLMT (verbal learning and memory test)   | vlmt_0011 – vlmt_0220  | total score : addition of the learning achievements of the 5  |

|   |                       |   |
|---|-----------------------|---|
|   |                       | rounds; delayed recall : number of words correctly recalled from the word list after a time delay; loss after delay : subtraction of the number of correctly recalled words in learning session 7 from the number of correctly recalled words in learning session 5; correct recognition : subtraction of the number of false positives and interference items from the number of correctly recognised words in the first list (i.e.: 18. recognition performance (W) - (19. interference + 20. false positives)). |
| BVMT-R (brief visuospatial memory test revised) | bmvt_0011 – bmvt_0150 | total score : addition of the points from all three trials; delayed recall : number of correctly remembered figures. (correct figure and correct place); percent retained : [delayed recall / (higher of trial 2 and trial 3)] x 100; recognition discrimination index : (recognition hits) - (recognition false alarms)  |

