| inflammatory biomarkers in serum and cerebrospinal fluid (white cell count, total protein, CSF/serum quotients of albumin (Qalb), lactate, oligoclonal IgG bands (OCB), cytokines))  | haem_0051-haem_0273, chem_0011-chem_0083, liq_0011-liq_0173  |  |
| MRI measures: grey matter volume, white matter volume, thalamus volume left and right, thalamic functional connectivity to sensomotoric cluster left and right, thalamic functional connectivity to visuo-occipital cluster left and right, EndoPAT Reactive Hyperemia Index (RHI) | gm_volume, wm_volume, thalamus_l_volume, thalamus_r_volume, thalamic_motor_l_fc, thalamic_motor_r_fc, thalamic_occipital_l_fc, thalamic_occipital_r_fc, endopat_rhi  |  |
| OCT: ganglion cell-inner plexiform layer (GCIPL), peripapillary retinal nerve fiber layer (pRNFL), foveal avascular zone (FAZ), vessel density   | gcipl, prnfl, faz, vessel_density_full   |  |
| CD11c Expressions (CD19+ B cells, IgD-CD27+ memory B cells), IgM Expressions, Activated canonical class-switched memory B cells  | z_cd11c_exp_cd19pl, z_cd11c_exp_igdmin_cd27plus_cd19pl, perc_cd11cpl_cd19pl, perc_cd11cpl_igdmin_cd27pl_cd19pl, z_igm_exp_cd19pl, z_igm_exp_igdmin_cd27pl_cd19pl, perc_igmpl_cd19pl, perc_igmpl_igdmin_cd27pl_cd19pl, perc_acsm_igdmin_igmmmin_cd27pl_cd11cmin_cd19pl, perc_cl_acsm_igdmin_cd27pl_cd19pl |  |
| Safety related endpoints   |  |  |

|  |                   |  |
|--|-------------------|--|
| Adverse events and severe adverse events | ae_0053, sae_0123 |  |
|--|-------------------|--|

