## 8 Handling of missing values

Missing data will be categorized according to Rubin as “missing completely at random”, “missing at random” and “missing not at random” (MCAR, MAR and MNAR) (RUBIN, 1976). For missing data in outcome variables, data will be imputed using multiple imputation by chained equations (mice) (Van Buuren & Van Buuren, 2012) with the R package MICE (van Buuren & Groothuis-Oudshoorn, 2011) with 30 imputed data sets, where appropriate is the assumption of MAR or MCAR is reasonable. It is planned to perform sensitivity analyses, in which the robustness of the inference will be investigated. Sensitivity analyses will be done using complete data without any imputation. The following variables will be used for the imputation process: all outcome variables, demographic variables age, sex, and BMI.

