### 9.2 Primary analysis

For the primary outcome, the Chalder Fatigue Scale at 2 months, descriptive statistics will be presented for both treatment arms. This will include the number of participants (n), mean, standard deviation (SD), median, interquartile range (IQR), minimum, and maximum for the continuous total score. Additionally, for the categorical responses (e.g., presence/absence of fatigue), frequencies and percentages will be reported.

Confirmatory analysis of the primary outcome will be conducted based on the full analysis set. An analysis of covariance (ANCOVA) will be conducted. The dependent variable is the Chalder Fatigue Score at day 60, independent variables include baseline Chalder Fatigue Score, treatment group (intervention / control), and age at baseline. The effect estimate for the treatment variable and the corresponding 95%CI will be reported. Sensitivity analysis will be done using the PPS without imputation of missing values.

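### Imputing Day-60 Chalder from every outcome variable, read by visit and domain, gives about 98 to 148 predictors for at most 66 patients

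*SAP*

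**What the plan says.** Section 8 plans imputation by chained equations with 30 imputed data sets for missing outcome data, and names the predictors: "The following variables will be used for the imputation process: all outcome variables, demographic variables age, sex, and BMI". It gives no correlation threshold, cap, restriction by visit or score, data layout or univariate imputation method. Sections 5.2, 9.2, 9.3 and 11 add nothing on these points; Section 11 names only the package.

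Section 5.2 runs the primary analysis on the FAS, "including the estimated values from multiple imputations for missing values". Section 9.2 gives that analysis its status: "Confirmatory analysis of the primary outcome will be conducted based on the full analysis set". The imputed Day-60 Chalder values therefore enter the main result directly.

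Section 7.3 lists outcomes with their visits, several at four or five post-baseline time points. Table 5 ("Table 5: primary and secondary outcome variables") sets the scoring. COMPASS-31 is "31 items in 6 domains, score by domain are rescaled ranging from 0 to 100", for PROMIS-29 "each of the 7 domains will be scored separately, transformation in standardized t-values", and the Fluge domains are also analysed separately. Imaging outcomes appear as individual variables, for example "gcipl, prnfl, faz, vessel_density_full".

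Section 4.2 randomises 44 and 22 patients and applies a general 20% drop-out, "resulting in expected group sample sizes of 35 and 18 patients, respectively".

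**The concern.** In chained equations, the model for Day-60 Chalder is fitted to the patients in whom that score is observed. If the coefficients outnumber those patients, least squares has no unique solution. The software must then shrink, drop columns or both, and its choices shape the imputed values. The SAP fixes none of these choices, so two analysts who both follow Section 8 could obtain different primary estimates.

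Some of the listed columns are also empty by design: PCFS outside PACS-CFS, optional neuropsychology and CSF, and grip strength and Schellong at month 6, which are done only on request. Section 8 does not say how these enter.

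**Working it through.** **Patients available.** Section 4.2: 0.8 × 44 = 35.2 and 0.8 × 22 = 17.6, rounded to 35 and 18, total 53. The SAP's precision figures follow from t × 5.8 × √(1/n₁ + 1/n₂). For 44/22 this gives 3.03, as stated. For 35/18 it gives 3.377, against 3.37 stated. The drop-out rate is not tied to Day 60, so 53 is only a guide; the firm upper limit is 66.

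**Clinical scores by visit** (post-baseline visits from Section 7.3, scores from Table 5; on-request month-6 tests left out at first):

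| Outcome | Scores × visits | Variables |
|---|---|---|
| Chalder, SF-36 physical, PEM, Bell | 4 × 5 | 20 |
| Fluge (four named domains) | 4 × 4 | 16 |
| COMPASS-31 | 6 × 4 | 24 |
| PROMIS-29 | 7 × 4 | 28 |
| Schellong, grip strength | 2 × 2 | 4 |
| 6MWT, MoCA, SDMT, PROMIS cognitive | 4 × 1 | 4 |
| **Total** | | **96** |

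Table 5 announces five Fluge domains but names four; four are counted. Grip strength has no row in Table 5 and is taken from Section 7.3.

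**Predictors for Day-60 Chalder** = outcomes − 1 (the target) + 3 (age, sex, BMI):

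- Clinical scores: 96 − 1 + 3 = 98.
- Adding PCFS at four visits: 98 + 4 = 102.
- Adding month-6 grip strength and Schellong: 102 + 2 = 104.
- Starting from 102 and adding neuropsychology (VLMT 4, BVMT-R 4, WAIS-IV 3, TAP 5, LPS 50+ 1, TMT 3, RWT 2, WST 1 = 23): 125.
- Adding the named MRI/EndoPAT (9), OCT (4) and B-cell (10) variables once each: 125 + 23 = 148.

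The autoantibody, immunoglobulin, haematology, chemistry and CSF ranges are not counted, so 148 is a low figure for the full list. Even 98 predictors need 99 coefficients with the intercept, against at most 66 patients.

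**Narrower readings.** One column per clinical instrument or test gives 14 + 8 − 1 + 3 = 24 predictors. Counting domains at a single visit gives 30 without neuropsychology and biomarkers, 53 with neuropsychology, and 76 with the named biomarkers as well. The SAP states none of these.

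**Sensitivity to handling (simulation).** Taken from the SAP: 44/22 patients, SD 5.8, and 13 missing from the drop-out rate. The true effect of −4.5 is the difference that Section 4.2 cites from an earlier study. Assumed: missing completely at random, baseline correlation 0.5, auxiliaries correlated 0.4 and fully observed, treatment arm in the model, predictive mean matching.

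- Small ridge against dropping collinear columns: estimate moved by 0.3 to 0.7 points.
- Reversing which columns survive, with 52 kept on 53 patients (53 − 52 − 1 = 0 residual degrees of freedom): median shift 0.5 to 0.6 points at 54 predictors and 0.8 at 69; 90th percentile 1.7 to 2.0.
- The same reversal with 35 columns kept: 0.33 at 54 predictors and 0.38 at 69.
- For comparison, a new random seed moved the estimate by 0.03 to 0.07 points. With 11 predictors, handling moved it by less than 0.1.

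**The case against.** The strongest counter-argument is that no analyst would load every column, and that a sensible narrow set fits easily: 24 predictors leave 53 − 24 − 1 = 28 residual degrees of freedom. That is true as a matter of practice. But Section 8 states a rule, and the narrow set is not that rule. A layout with one row per patient and visit would also reduce the columns, but no layout is stated.

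A reader might try to show the problem with a minimal count: one column per instrument or laboratory row, plus each named imaging and B-cell variable. That gives 54 predictors against 53 patients. The documents do not support resting the case on it. It mixes counting units; one column per group throughout gives only 34 predictors. It counts the ak_ autoantibody range twice, since that range appears in two rows of Table 5. It includes grip strength, which has no row there. It also treats the general drop-out rate as a Day-60 figure: if 10 or fewer patients lacked the score, 55 coefficients could be fitted. The by-visit, by-domain count needs none of this, because it exceeds 66.

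The larger simulated shifts come from a saturated cut to 52 columns, a rule that the SAP does not contain, and they shrink under a milder cut. The auxiliaries were assumed fully observed, which is unlikely for patients who drop out. That objection stands, and the size is stated accordingly.

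The complete-data and PPS analyses could reveal a discrepancy. They do not determine the primary estimate.

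**Conclusion.** The point holds. Read by visit and domain, Section 8 specifies a Day-60 Chalder imputation model with about 98 to 104 predictors from clinical scores alone and about 148 with neuropsychology and the named biomarkers, for at most 66 patients. That model has no unique fit, so the confirmatory estimate depends in part on unspecified software handling.

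The size is modest and conditional. Under the assumed correlations, handling moves the treatment estimate by some tenths of a point, and by more under a saturated cut. The SAP's own benchmarks are a minimal important difference of 2.3 to 3.3 points and an expected half-width of 3.37.

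A reader might infer that the primary result will be biased toward no effect, or that its interval will be too wide or too narrow. Neither follows. Some simulated settings gave mean estimates nearer zero, but a less saturated cut largely removed this. Interval widths moved in both directions.

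**What to change.** Replace the open-ended reference to every outcome with a short prespecified predictor set for each imputed endpoint. For Day-60 Chalder this could be:

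- the ANCOVA variables: treatment group, baseline Chalder and age (3);
- Chalder at EOT and months 1, 4 and 6 (4);
- sex and BMI (2);
- at most a few prespecified correlated scores.

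That is 9 predictors before the last item. With two added scores it is 11, leaving 53 − 11 − 1 = 41 residual degrees of freedom if 53 patients are observed. The added scores should be chosen with an eye to which are likely to be present when Day-60 Chalder is missing, since questionnaires from the same visit may be lost together. A minimum-correlation rule with a cap on the number of predictors would also do.

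State the univariate imputation method and the data layout. Exclude from the primary-outcome model the columns that are empty by design: PCFS outside PACS-CFS, optional neuropsychology and CSF, and on-request month-6 grip strength and Schellong.

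The cost is SAP wording and a predictor matrix, with no change to trial conduct. The downside is that some auxiliary information goes unused.

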## 9 Statistical analyses / methods

### 9.1 Demography and baseline characteristics

Demography and baseline characteristics will be reported for the total population and by treatment arm using descriptive statistical summary measures. No statistical test will be performed to compare baseline characteristics between randomized treatment groups. For continuous variables, mean with standard deviation (SD), median, interquartile range (IQR), minimum, maximum will be given depending on the distribution of the respective characteristic. For categorical data absolute and relative frequencies are given for each category.

### 9.2 Primary analysis

For the primary outcome, the Chalder Fatigue Scale at 2 months, descriptive statistics will be presented for both treatment arms. This will include the number of participants (n), mean, standard deviation (SD), median, interquartile range (IQR), minimum, and maximum for the continuous total score. Additionally, for the categorical responses (e.g., presence/absence of fatigue), frequencies and percentages will be reported.

Confirmatory analysis of the primary outcome will be conducted based on the full analysis set. An analysis of covariance (ANCOVA) will be conducted. The dependent variable is the Chalder Fatigue Score at day 60, independent variables include baseline Chalder Fatigue Score, treatment group (intervention / control), and age at baseline. The effect estimate for the treatment variable and the corresponding 95%CI will be reported. Sensitivity analysis will be done using the PPS without imputation of missing values.

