### 9.3 Secondary analyses

For all secondary endpoints, descriptive statistics will be calculated and presented at each time point of measurement for both treatment groups. For continuous secondary outcomes, this will include the mean, standard deviation, median, interquartile range, minimum, and maximum. For categorical or ordinal secondary outcomes, frequencies and percentages will be reported. These descriptive summaries will be presented in tabular format, and appropriate graphical representations, such as line plots for longitudinal data, bar charts, or box plots, will be utilized to visually depict trends, distributions, and differences between treatment arms across all assessment time points. For all secondary endpoints, analysis of

covariance (ANCOVA) models will be employed, analogous to the approach for the primary outcome. The choice of link function will be tailored to the specific nature of each outcome variable (e.g., linear for continuous outcomes, binary logistic for dichotomous outcomes, or ordinal for ordered categorical outcomes). In instances of repeated measures, mixed-effects regression models will be utilized, incorporating random intercepts for individual participants to account for within-subject correlation. Each model will include the respective baseline value of the endpoint, age at baseline, and treatment group as fixed effects. Effect estimates for the treatment variable, along with their 95% confidence intervals (CI), will be reported. All analyses will be conducted using the Full Analysis Set (FAS). Sensitivity analyses will be performed using the Per-Protocol Set (PPS), without imputation of missing values, to assess the robustness of the findings.

**Responder analysis:** Explorative analyses comparing responders and non-responders in both groups regarding PCS-associated signature at baseline: CD11c and IgM expression and an aCSM frequency. For this analysis a binary logistic regression model will be implemented with the responder (yes/no) variable as the dependent variable, the PCS-associated signature at baseline, the group and the interaction term between PCS-signature at baseline and group as independent variables.

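### The 95% CI of the primary ANCOVA relies on equal variances under 2:1 allocation and no planned analysis relaxes this; the size of the error depends on an SD ratio that the SAP does not give

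*SAP*

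**What the plan says.** Section 9.2 describes the primary analysis in one line, "An analysis of covariance (ANCOVA) will be conducted". The outcome is the day-60 Chalder score, and the "independent variables include baseline Chalder Fatigue Score, treatment group (intervention / control), and age at baseline". On output it says "The effect estimate for the treatment variable and the corresponding 95%CI will be reported". It mentions no robust standard error, arm-specific variance or check of equal variances.

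Section 4.2 sets the group sizes: patients are "allocated in a 2:1 ratio: immunoabsorption (IA) group: 44 patients vs. sham group: 22 patients". Its precision calculation uses "a common standard deviation of 5.8 as provided for patient with CFS/ME". The only other SD in the document is also there: "for a healthy sample a mean value of 14.2 (with a standard deviation of 4.6) was observed".

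The sensitivity analyses (the per-protocol set in 5.2 and 9.2, complete data without imputation in section 8) change the patients or the imputation and keep the model. Section 9.3 carries the same ANCOVA to the continuous secondary endpoints.

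**The concern.** A standard ANCOVA estimates one residual variance from all patients and uses it for both arms. With equal arms this does little harm. With 2:1 allocation the larger arm dominates the pooled variance, while the smaller arm dominates the true variance of the difference. A difference in spread therefore biases the standard error, and the direction depends on which arm varies more.

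The CI for the treatment effect is the trial's main result, and the sample table 14.2.3 puts a p-value beside it. If IA varies more, the CI stays valid but loses power. If sham varies more, it is too narrow and false positives exceed 5%. The direction cannot be known in advance, so the variance method is better fixed before unblinding than chosen after the spread has been seen.

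**Working it through.** **The plan's own figure.** The half-width is t(0.975, n1+n2−2) × 5.8 × √(1/n1 + 1/n2).
- 44/22: 1.998 × 5.8 × 0.2611 = 3.03, as stated.
- 35/18 (after 20% drop-out): 2.008 × 5.8 × 0.2900 = 3.377, stated as 3.37, a rounding difference only.

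The planning calculation is thus the pooled-variance formula with a common SD.

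**Why allocation matters.** The pooled variance of the difference is sp² × (1/n1 + 1/n2), with sp² = [(n1−1)s1² + (n2−1)s2²]/(n1+n2−2). The true variance is s1²/n1 + s2²/n2. At 33/33 both equal (s1² + s2²)/33, so unequal spread cancels. At 44/22 it does not.

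**Worked case, SD ratio 1.4 at 44/22** (SD of the less variable arm set to 1, so the squared ratio is 1.96):
- More spread in IA: sp² = (43 × 1.96 + 21)/64 = 1.645. Pooled variance 1.645 × 0.06818 = 0.1122. True variance 1.96/44 + 1/22 = 0.0900. SE ratio √(0.1122/0.0900) = 1.116, so the SE is 11.6% too large.
- More spread in sham: sp² = (43 + 21 × 1.96)/64 = 1.315. Pooled variance 0.0897. True variance 1/44 + 1.96/22 = 0.1118. SE ratio 0.895. Approximate coverage 2Φ(1.998 × 0.895) − 1 = 92.6%.

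**Range at 44/22.** The simulation runs the planned model (baseline, age, group) with 60,000 runs for each unequal-variance scenario. The ratio 1.26 is 5.8/4.6, used only as an illustration.

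| SD ratio | More spread in IA: SE too large, analytic (simulated) | More spread in sham: coverage, analytic (simulated) |
|---|---|---|
| 1.0 | 0% | 95% (95.0%) |
| 1.1 | 3.3% | 94.7% |
| 1.26 | 8.0% (7.1%) | 93.6% (93.3%) |
| 1.4 | 11.6% (11.0%) | 92.6% (92.4%) |
| 1.5 | 14.0% (13.0%) | 92.0% (91.5%) |
| 2.0 | 22.8% | 89.6% |

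The analytic coverage puts a t quantile into a normal distribution and so reads slightly high: it would give 95.4% at ratio 1. Using the t distribution with 64 degrees of freedom throughout gives 94.25% at ratio 1.1 and 89.1% at ratio 2. At 35/18 and ratio 1.4 the figures are 11.2% (simulated 9.9%) and 92.9% (simulated 92.3%).

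**Effect of the fix.** Over SD ratios 1.26 to 1.5, both directions and both sample sizes, simulated coverage is 95.1-95.8% with HC3 and 94.3-95.1% with HC2. Mean half-widths at ratio 1.4 and 44/22, with residual SD 5.8 in the less variable arm:
- More spread in IA: 3.93 ordinary, 3.67 HC3, 3.55 HC2.
- More spread in sham: 3.51 ordinary (coverage 92.4%), 4.03 HC3 (95.4%), 3.88 HC2 (94.6%).

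These simulations use complete data. The multiple imputation step was not simulated; 35/18 enters only as a smaller sample.

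**The case against.** **The SAP does not state that variance is pooled.** True. It is inferred from the default of a standard ANCOVA and from the planning SD. But no text points elsewhere, and an analyst following 9.2 would get the pooled version.

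**The larger figures are not this trial's.** This stands. A reader might take 11% and 92% as the expected error, but they need an SD ratio of about 1.4, which the document does not supply. One route to it is that 35% of IA patients improve by 10 points and nobody on sham does. With an assumed baseline to day-60 correlation of 0.5, the residual SD is 5.8 × √(1 − 0.25) = 5.02, and the IA SD becomes √(5.02² + 0.35 × 0.65 × 10²) = 6.9. Ten points is about the whole gap between patients and healthy people in 4.2 (24.4 versus 14.2). Milder versions matter little. With a 6-point split, coverage is 95.8-95.9% (split in IA) or 94.2% (split in sham). With 15% responders on sham as well, the SE excess falls from 11% to 4.0%.

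**A reader might infer that the SAP expects responders in the IA arm only.** It does not say so. Section 9.3 describes "Explorative analyses comparing responders and non-responders in both groups regarding PCS-associated signature at baseline". That is an exploratory yes/no variable, and it allows for sham responders. Dichotomising an outcome does not assert a mixture distribution.

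**The harmful direction has no stated mechanism.** The two SDs in 4.2 come from separate populations. Taken as a hint that scores nearer the healthy level vary less, they would make sham the more variable arm, opposite to the responder argument. This shows that the sign is unknown; it does not predict either direction.

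**Model-based ANCOVA is a standard choice, and section 4 calls the trial exploratory.** Both are fair, and 9.2 already tabulates the SD by arm, so a marked difference would be seen. But 9.2 also calls this analysis confirmatory, and seeing unequal spread afterwards does not correct the interval.

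**Conclusion.** The point holds as a calibration gap, and it is an inexpensive improvement to make. The primary CI depends on equal residual variances under 44:22 allocation, and no planned analysis relaxes that. If the variances are equal, the planned CI is correct. If not, the error is small at an SD ratio of 1.1, about 7% too wide or 93% coverage at 1.26, about 11% or 92% at 1.4, and about 23% or 89 to 90% at 2. The first figure applies when IA varies more and the second when sham does.

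These sizes rest on assumed SD ratios and on the default reading of 9.2. The documents do not support the stronger conclusions that the trial will show an error of 11% or 92%, that a responder mixture is planned for, or that sham will be the more variable arm.

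**What to change.** Add to 9.2: the 95% CI for the treatment effect uses heteroscedasticity-consistent standard errors (HC3, or HC2), computed in each imputed data set and then pooled, with the model-based CI shown alongside. A model with arm-specific residual variances is an acceptable alternative. Name one method in advance, apply it also to the linear ANCOVAs in 9.3, and list the software used for it in section 11.

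The cost is one sentence and one option in R. With HC3 the CI is about 3-4% wider if the variances are equal: assuming a residual SD of about 5.0, 2.75 against 2.66 at 44/22 and 3.10 against 2.97 at 35/18. HC2 costs about 0% in that case, but its coverage is about 94-95% at SD ratios up to 1.5, where HC3 holds at least 95%.
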